The commissioning brief emphasises the need for trials within NCAs to test the principles of effective communication of NCA data to key audiences. We will use the findings of Phase 4 to determine for whom and in what contexts a trial of QualDash is appropriate. This avoids the cost of a trial if QualDash is found to be ineffective while, if the results of Phase 4 suggest QualDash does provide benefit, we will be able to design a trial that is fit for purpose, with high internal and external validity, for which subsequent funding would be sought.^{113,114}

Progression criteria will be: (i) QualDash is used by 50% or more of the intended users; (ii) data completeness in the NCA improves or remains the same; and (iii) participants perceive QualDash to be useful and express the intention to continue using it after the study period. Criteria (i) and (iii) are concerned with acceptability and uptake of the intervention, and therefore have implications for recruitment to a trial. The second criterion is concerned with ensuring that the intervention does not have unintended negative consequences which would affect both the success of the intervention (as QualDash will be less useful if data completeness is reduced) and the feasibility of outcome assessment. The third criterion is also concerned with participants' perceptions of the impact of QualDash on care. While not formally assessed as part of the progression criteria, the impact of QualDash on processes of care as identified in the CITS will also be considered in determining whether a future CRT is justified. A traffic light system will be used to determine if a trial is feasible (green), feasible with modifications to QualDash and/or the implementation strategy (amber), or not feasible (red). 113,115

If a trial is found to be feasible, a CRT will be designed. It is anticipated that the primary outcome will be a patient outcome. Data from the CITS will be used to inform the selection of NCAs to be included in the trial (MINAP and/or PICANet) and will provide information about variability of outcomes and about how long a trial intervention period would need to be. Findings from the multi-site case study will be used to inform the selection of categories of user to be included in the trial and, associated with this, the level of randomisation (Trust, hospital, or ward).

If the feasibility assessment indicates that QualDash and/or the implementation strategy need to be modified, Phase 4 findings will be used to determine what those modifications should be, while also identifying components of QualDash and the implementation strategy that, being associated with mechanisms that produce desired outcomes, should be preserved in the trial.

In addition, two focus groups will be undertaken in the Phase to assess the extent to which QualDash and the program theory are applicable to other NCAs.

Team

Trial feasibility assessment and design will be led by AF, working in collaboration with RR and the SoH RF, with support from a statistician and trial manager from the Leeds Institute for Clinical Trials Research (LICTR). If modifications to QualDash are required, these will be undertaken by the SoC RF, under the guidance of RAR. If modifications to the implementation strategy are required, these will be undertaken by the SoH RF, under the guidance of RR. RR and the SoH RF will undertake the focus groups.

Sample: Two focus groups will be held. In the first focus group, we will bring together quality sub-committee members from across the five sites. In the second focus group, we will bring together suppliers of intermittent audits.

Data collection: The focus groups will be moderated by RR, who will encourage participants to discuss differences in their opinions. The SoH RF will make notes on the order of speakers and non-verbal interaction. Each focus group will be audio recorded. In the first focus group, participants will be asked to discuss the extent to which QualDash would be suitable for NCAA, NACR, the Elective Surgery National PROMs Programme, and the BAUS audits. The discussion will not just consider the features of QualDash and how they may need to be adapted for the particular types of data held within these three audits, but also contextual factors that may impact use of QualDash for engaging with these audits. In the second focus group, participants will be asked to discuss whether and how QualDash might be adapted to provide value to intermittent audits.

Analysis: The audio recordings will be transcribed verbatim, using the notes to identify speakers, and then annotated with notes of the non-verbal interaction. Analysis of the data will be conducted using framework analysis as described above. This analysis will be used to make further refinements to the QualDash program theory.

Outputs

- Assessment of the feasibility of a CRT of QualDash; and
- If criteria for progression are met, design for a CRT of QualDash.

DISSEMINATION AND PROJECTED OUTPUTS

The main outputs will be: i) a program theory that explains how and in what contexts QualDash use leads to improvements in care quality; ii) based on the QualDash program theory, a requirements specification to support design of QualDash, generalisable to all NCAs, delivered by end of month 6 with revisions as the project progresses; iii) a technical specification for QualDash, delivered by end of month 12 with revisions as the project progresses; iv) an interactive web-based quality dashboard for clinical teams, quality sub-committees, boards, and commissioners, using novel visualisation techniques and tailored to meet the needs of different users, that can be adapted for all NCAs; v) a QualDash implementation strategy, the success of which is not dependent on involvement in design of QualDash; vi) evidence regarding how and in what contexts use of QualDash leads to improvements in care quality; vii) assessment of the feasibility of a CRT of QualDash; and, if progression criteria are met, viii) design for a CRT of QualDash.

Outputs i-iii will be sent to HQIP and NCA suppliers and will be made available on a dedicated project website. Outputs i and ii will enable suppliers of other NCAs to draw on our findings to inform the design of feedback they provide, and output ii can be used by suppliers if employing a commercial company to develop a quality dashboard. Output iii will support suppliers of other NCAs to develop their own quality dashboards based on the design of QualDash. We will hold an end of project dissemination event for NCA suppliers, with presentations video recorded and made available on the project website.

Other dissemination activities will include Open Access publications in a range of academic journals (e.g. BMJ Quality & Safety, Implementation Science, Journal of the American Medical Informatics Association), and presentation of findings at a national conference, such as the HSRUK Symposium or the HQIP-sponsored Clinical Audit for Improvement conference.

PLAN OF INVESTIGATION AND TIMETABLE

The project will be for 33 months. The timetable below describes the key tasks to be completed within the project and the timing of key milestones.

	Months	:										
	Pre-	1-3	4-6	7-9	10-	13-	16-	19-	22-	25-	28-	31-
	study				12	15	18	21	24	27	30	33
Tasks												
Ethics & R&D approval												
PHASE 1				_								
Interviews across 5												
Trusts			-									
Workshop with NCA												
suppliers												
PHASE 2												
Iterative development												
Controlled user												
experiment PHASE 3												
QualDash												
implementation												
PHASE 4												
QualDash evaluation –												
data collection												
QualDash evaluation -												
analysis												
PHASE 5												
Trial feasibility												
assessment & design												
Focus groups												
Final report												
Milestones												
Requirements			*									
specification delivered												
Technical specification					*							
delivered												
Implementation strategy delivered						*						
QualDash software												
release						*						*
QualDash evaluation												
data collection										*		
complete												
QualDash evaluation											4	
analysis complete											*	
Progress reports			*		*		*		*	•	*	

PROJECT MANAGEMENT

All applicants will be part of the Project Management Group (PMG), chaired by RR (PI). This group will initially meet monthly and then every two months, where the progress of the research will be reported and decisions regarding next steps will be made. Between meetings, email will be used to keep the PMG up to date. A meeting with RR, RAR, JK, and the research staff will be held fortnightly to monitor the progress of the research. In addition, RR will meet at least weekly with the SoH research staff and RAR will meet at least weekly with the SoC RF. Other members of the PMG will be involved in these meetings as and when their methodological and/or subject expertise is needed.

We will also convene a Study Steering Committee (SSC). The following people have agreed to be on the SSC: [name] (University of Leicester, expertise in relevant social science theories and the conduct of ethnographic studies of quality and safety); [name] (University of Leeds, expertise in realist evaluation); [name] (Swansea University, MINAP clinical lead). We will have a representative of HQIP on the SSC ([name], [name], or [name]). We will also invite representatives of NCAA, NACR, and the Elective Surgery National PROMs Programme to join the SSC. We will appoint an NHS manager with responsibility for audit via the Yorkshire & Humber Effectiveness & Audit Regional Network, an NHS IT manager, and an expert in CITS. We will ask our LAG to nominate a member to sit on the SSC. SSC meetings will take place at key points in the project: shortly

after the beginning of the project; at the end of Phase 1, to discuss the requirements specification and its implications for the design of QualDash; at the end of Phase 3, to review the Phase 4 evaluation design in light of the revised QualDash program theory; and at the end of Phase 4, to discuss the findings and appropriate steps forward. The dissemination plan will be discussed at the first SSC meeting and will be a regular item on the agenda of the SSC meetings.

APPROVAL BY ETHICS COMMITTEES

We propose to carry out data collection across five NHS hospital Trusts, involving staff in the study. We will also be working with anonymised routinely collected data. The research team has considerable relevant experience, both in carrying out qualitative research in such settings and in the use of routinely collected data. NHS Research Ethics Committee approval will be sought. We have a draft ethics application which will be submitted by the end of May 2017. R&D governance approval will then be sought. Both MINAP and PICANet data are already held securely within the University of Leeds. We are aware of the third Caldicott report and will ensure that our data handling arrangements are compliant with any new guidance published in 2016/2017.

PATIENT AND PUBLIC INVOLVEMENT

A draft of the plain English summary was circulated to the Patient and Public Involvement (PPI) Group of our current dashboards study and discussed at the PPI meeting in April 2016. A LAG will be established, with participants recruited from the PPI Group of our current study, lay members of PICANet's Paediatric Intensive Care Families Group, and lay members of the MINAP Steering Group. LAG members will: Advise on data collection, e.g. review interview topic guides; Participate in a focus group to inform the design of QualDash; Participate in the controlled user experiment; Contribute to the design of the QualDash evaluation, e.g. selection of measures for the CITS; Provide their perspective on findings; Advise on dissemination of findings to relevant interest groups. They will also contribute to the creation of outputs, e.g. reviewing the requirements specification and user guide for comprehensibility. Five LAG meetings will be held over the course of the project, with the LAG also meeting to participate in the co-design activities and the controlled user experiment and with additional communication with members via telephone and email as the need arises. Four of the meetings will be scheduled to occur in advance of the SSC meetings, so that feedback from the LAG can be fed into the SSC meetings. An additional meeting will be held during Phase 1, prior to the workshop with NCA suppliers, for reviewing the requirements specification. A training session will be organised and de-briefing sessions will be held after activities to gather feedback on the process. This approach builds on successful PPI methods used in previous HS&DR projects. PPI will benefit the process and outputs of the project by: ensuring the topics explored in interviews include those that matter to patients/carers; making the design of QualDash more patient friendly; ensuring the measures used in the CITS are ones that matter to patients/carers; providing a more nuanced analysis (e.g. challenging clinicians' assumptions); ensuring comprehensibility of project materials; making communication of findings to the general public more effective. 116

EXPERTISE AND JUSTIFICATION OF SUPPORT REQUIRED Expertise

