To ensure the study generates findings that are generalisable beyond a single NCA, we have chosen to work with two NCAs, MINAP and PICANet. MINAP and PICANet are delivered by different suppliers and involve different clinical specialties working with different patient groups, multiple professional groups (medical and nursing), and include multiple types of measures (structure, process, and outcome). They also differ in data quality and completeness. MINAP has been running continuously since 2000, delivered by the National Institute for Cardiovascular Outcomes Research, and data are contributed by all hospitals in England, Wales and Northern Ireland that admit patients with acute coronary syndromes. PICANet was set up in 2002 by the Universities of Leeds, Leicester and Sheffield and contains data from all NHS Paediatric Intensive Care Units (PICUs) in England and Wales.

There are three main funding arrangements for independent NCAs: subscription by NHS Trusts; funded by a charity or professional body; or funded by NHS England. To explore the impact of funding arrangements, in Phase 1 we will also gather data on the National Cardiac Arrest Audit (NCAA; funded by Trust subscription), the National Audit of Cardiac Rehabilitation (NACR; funded by the British Heart Foundation), and the Elective Surgery National PROMs Programme

(funded by NHS England). There are a number of independent surgery NCAs where participation is at the individual clinician, rather than Trust, level; to understand the impact of this difference, in Phase 1 we will gather data about the British Association of Urological Surgeons (BAUS) audits. In Phase 5, we will explore the applicability of QualDash to those independent NCAs where data is collected intermittently rather than continuously,

We will work with three NHS acute Trusts (sites A-C) that participate in both MINAP and PICANet. These Trusts have been selected to ensure variation in key outcome measures (MINAP: 30 day mortality for ST-elevation myocardial infarction (STEMI) patients; PICANet: risk adjusted standardised mortality ratio), as shown in Table 1.

Because Trusts that participate in PICANet tend to be larger and to be teaching hospitals, they are not representative of the range of Trusts that participate in MINAP. Therefore, MINAP use will also be studied in two district general hospitals (DGHs; sites D-E) that do not have a PICU. These have been selected to ensure variation in the same key MINAP measure.

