- A program theory that explains how and in what contexts QualDash use leads to improvements in care quality; and
- A requirements specification to support design of QualDash, generalisable to all NCAs.

Phase 2: Design of QualDash *Objective*

To use the program theory to co-design QualDash (Objective 2).

Summary of method

Phase 2 represents the conceptual design, prototyping and software development stages. QualDash will be developed iteratively, with input from a series of interactive focus groups. Focus groups are group interviews, coordinated by a moderator, that concentrate on a particular topic and generate qualitative data through discussion between

participants.⁸⁸ Differences in participants' opinions and accounts can be explored, helping to draw out the needs of different categories of user and to refine our understanding of the contextual factors that are likely to affect QualDash use.⁸⁹ Focus groups enable group ownership of problems and solutions and so are appropriate for the purpose of codesign.⁸⁸ It is important to ensure that the focus group is organised in such a way that participants are actively involved in the process of design, rather than just consulted,⁷ so the focus groups will incorporate co-design activities such as cognitive walkthroughs and creating storyboards and paper-based prototypes. This will be complemented by ethnographic observation of meetings where quality and safety are discussed, to understand the functionality that QualDash needs to provide to support discussion of NCA data in those meetings and how QualDash may best be incorporated into those meetings.

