Sample: While all five Trusts will be involved in the co-design process, through participating in the Phase 1 interviews, co-designing the implementation strategy in Phase 3, and providing feedback on QualDash in Phase 4, we are intentionally only involving one Trust in Phase 2 so that we can assess, in Phase 4, to what extent the success of QualDash is dependent on this level of staff involvement in the design process. We anticipate that a minimum of three focus groups will be held (more if separate focus groups are held for MINAP and PICANet). An additional focus group will be held with our LAG, to gain a patient and carer perspective on the proposed designs. Guidance on focus groups suggests 8-12 participants as a suitable number.⁸⁸ While generally homogenous groups are recommended, it can be beneficial to bring together a diverse group to maximise exploration of different perspectives;⁸⁹ to support the identification of similarities and differences in the needs and preferences of our different stakeholders, the first focus group will bring together a purposive sample of members of the cardiology and PICU clinical teams, the quality subcommittee, and the Trust board, and local commissioners (total n=12). On the basis of this focus group we will decide whether in the subsequent focus groups there would be benefit in holding separate focus groups relating to MINAP and PICANet.

Data collection: The SoH RF will take on the role of moderator, assisted by the SoH RA who will make notes on the order of speakers and non-verbal interaction (e.g. body language suggesting lack of engagement). 88,90 Each focus group will be audio recorded.

Co-design requires careful preparation but also a level of flexibility, to allow participants involvement in the design of the approach as well as the intervention. While open to revision and further specification, we plan to move from

developing paper-based storyboards and prototypes with participants (focus group 1), through to rapid prototyping where prototypes are purposely ambiguous and incomplete to encourage design input from participants (focus group 2), through to high fidelity prototypes (focus group 3). Discussion of the QualDash prototypes will include discussion of how comprehensible they are (in terms of both the functionality and the presentation of the data) and alternative ways in which the data could be presented.

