Throughout the focus groups the moderator will encourage participants to discuss differences in their opinions.⁸⁹ At the end of each focus group, the moderator will present any tentatively identified issues to participants for confirmation or clarification.⁹⁰

Analysis: The audio recordings will be transcribed verbatim, using the notes to identify speakers, and then annotated with notes of the non-verbal interaction. Analysis of the data will be conducted after each focus group using framework analysis as described above. This analysis will be used to make further refinements to the QualDash program theory and determine priorities for the next iteration of the QualDash prototypes.

Software development: The SoC RF will develop the QualDash software in two stages. The first (months 1-12) will turn the focus group outputs into high fidelity prototypes that implement the most important functionality identified in Phase 1, and then a version of QualDash that is suitable for evaluation by Trusts and CCGs in Phase 4. The key novelty of QualDash's design will come from the way we present data in visualisations, tailored to the needs of different users, and allow users to interact with those visualisations. The practicality of QualDash will be ensured through discussion with representatives from the Trusts' IT departments. The second stage of development (months 16-33) will incorporate feedback from the Phase 4 evaluation and functionality identified as important during the requirements prioritisation but initially omitted due to time constraints.

2b. Observation of meetings

Sampling: In each site, we will aim to observe at least one meeting at ward, quality sub-committee, Trust board, and CCG level.

Data collection: Researchers will observe the meetings, recording their observations in fieldnotes, to be written up in detail as soon after data collection as possible.

Analysis: An iterative approach to data collection and analysis will be taken, to feed in to the ongoing development of QualDash and to enable the gathering of further data in light of emerging themes. Fieldnotes will be entered into NVivo 10. Analysis of the data will be conducted using framework analysis as described above. This analysis will be used to make further refinements to the QualDash program theory and the requirements specification.

2c. Controlled user experiment

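### Section 2a says Phase 2 involves one Trust, but section 2b takes design information from all five sites, so Phase 4 can compare only focus-group co-design with interview- and observation-informed design

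*Protocol*

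**What the plan says.** Section 2a (Sample) lists how all five Trusts take part in co-design: "through participating in the Phase 1 interviews, co-designing the implementation strategy in Phase 3, and providing feedback on QualDash in Phase 4". Phase 2 is not on that list, and the text gives the reason: "we are intentionally only involving one Trust in Phase 2 so that we can assess, in Phase 4" the extent to which success "is dependent on this level of staff involvement in the design process".

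Section 2b, which the version table shows was added in version 2.0, belongs to the same phase. Its sampling rule is: "In each site, we will aim to observe at least one meeting at ward, quality sub-committee, Trust board, and CCG level". The Setting/context section defines the sites: "We will work with three NHS acute Trusts (sites A-C) that participate in both MINAP and PICANet", and "MINAP use will also be studied in two district general hospitals (DGHs; sites D-E) that do not have a PICU". That makes five.

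The 2b observations have a design purpose. The Phase 2 summary says they are made "to understand the functionality that QualDash needs to provide to support discussion of NCA data in those meetings". The 2b analysis paragraph says collection and analysis run iteratively "to feed in to the ongoing development of QualDash", and that the results refine the program theory and the requirements specification.

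Under Dissemination and projected outputs, output v is an implementation strategy whose success is described as not depending on having been involved in designing QualDash.

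**The concern.** Sections 2a and 2b are both current text. Taken literally, one says that a single Trust is involved in Phase 2 and the other collects Phase 2 data from five. The one-Trust rule is not a convenience: it is the stated basis for an inference in Phase 4. If the exposure delivered differs from the exposure described, the conclusion has to follow the exposure delivered.

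Involvement in design could help a Trust in at least two ways. Staff who co-design may feel ownership, and the product may fit local practice better. The focus groups bear on both. The 2b observations do not create ownership, but they do bear on fit, because the functionality is meant to suit the meetings observed. If all five Trusts did similarly well, one reader would conclude that design involvement is unnecessary. Another could say that QualDash was shaped around the other four Trusts too. The plan as worded does not separate these readings, and output v is phrased in the terms of the first. A later adopter would have had neither focus groups nor pre-design interviews and observation, so the difference matters for roll-out.

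**Working it through.** No power or sample-size figure is involved. The check sets the sections side by side and counts.

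**1. Trusts contributing to Phase 2**

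| Source | Inside Phase 2 | Outside Phase 2 |
|---|---|---|
| 2a, as worded | 1 | 5 − 1 = 4 |
| 2b, as worded (sites A–C and D–E: 3 + 2 = 5) | 5 | 0 |
| Focus groups alone | 1 | 4 |

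The first two rows conflict. The third shows what is left of the intended contrast.

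**2. Does 2b count as design input?** By its stated purpose it does: functionality, ongoing development and the requirements specification are all named. Nothing in the Protocol keeps the other four sites' fieldnotes out of the version evaluated in Phase 4. It does not make the observed staff co-designers. Researchers watch and write notes, and no one at those sites works on a storyboard or prototype under 2b.

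**3. How much is planned under 2b?** If the sampling rule is read as one meeting at each of the four levels named, the aim is at least 4 × 5 = 20 meetings, of which 4 × 4 = 16 are at the other four sites.

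**4. Is 2b the only such route?** No. Section 1a plans 3 × (12 + 2) + 2 × (7 + 1) = 42 + 16 = 58 interviews across all five Trusts and their commissioners. Participants are asked what QualDash would have to offer, and the results become the requirements specification. The first Phase 2 focus group includes PICU staff, so the co-design Trust must be one of sites A–C, with 14 of the 58 interviews. The other four Trusts then supply 58 − 14 = 44. Design information from those Trusts therefore existed before 2b was added, and 2a acknowledges it.

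**5. What the design delivers**

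| Route into the design before the Phase 4 release | Co-design Trust | Other four |
|---|---|---|
| Phase 1 interviews | yes | yes |
| Phase 2 focus groups (2a) | yes | no |
| Phase 2 meeting observation (2b) | yes | yes |

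The two groups differ on the focus-group row. Phase 4 can speak to that row. No group has a no in every row, so Phase 4 has no information on Trusts without design input.

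**The case against.** The strongest reply is that section 2a never sets an involved Trust against uninvolved ones. It says that all five take part in co-design, and the question it poses concerns a particular degree of staff involvement. The restriction appears in the focus-group section, and the summary and the design framework also tie it to the focus groups. Being observed in a meeting is not staff involvement in design. On this reading the 1-versus-4 split is intact and the conflict is a matter of wording. Phase 1 had already given every Trust a hand in the requirements, so 2b adds to a known feature. Nor does the Protocol set an estimator for this comparison: context is weighed by narrative analysis in the multi-site case study, which can describe the different exposures.

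Most of this stands. A reader might infer from the zero Trusts outside Phase 2 that the contrast is lost; the documents do not support that, because focus-group co-design stays in one Trust. A reader might also attach a dilution percentage, but nothing in the Protocol informs one. A third tempting step is to withhold four sites' fieldnotes from the developers. That would remove the stated purpose of 2b at those sites and leave the Phase 1 route open. It would also leak, since the program theory that the fieldnotes refine is itself the basis for the design.

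The reply does not remove the mismatch. Section 2a says Phase 2, not focus groups, and its list of shared routes omits 2b. Output v still speaks of involvement in design without qualification.

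**Conclusion.** The point holds as a conflict in the description of exposure and a limit on what Phase 4 may conclude. Sections 2a and 2b disagree on whether 1 or 5 Trusts contribute to Phase 2. The contrast actually available is focus-group co-design (1 Trust) against design informed by interviews and observation (4 Trusts). Similar success in the other four could show at most that focus-group co-design was not needed on top of those routes. It could not show that success is independent of design involvement, nor speak for Trusts with no design input. The size of any weakening caused by 2b cannot be derived from the Protocol.

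This rests on two readings: that a site in 2b means each of A to E, as Setting/context defines it, and that the 2b fieldnotes are used as the 2b analysis paragraph says.

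**What to change.** Reconcile sections 2a and 2b before Phase 4 results are known:

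- In 2a, state that the one-Trust restriction applies to focus-group co-design, and define the Phase 4 contrast as focus-group co-design versus interview- and observation-informed design.
- Add the 2b meeting observations to the list in 2a of routes by which all five Trusts contribute.
- Limit the Phase 4 conclusion and output v to that contrast, and make no claim about Trusts that had no input to the design.

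This needs wording changes only. No data are lost, and the 2b observations can go ahead as planned at every site. The cost is a narrower conclusion: the project could no longer present its implementation strategy as shown to succeed irrespective of design involvement.
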